#### 13.2.3. Recording Adverse Events

Investigators will monitor all subjects for AEs during the trial and establish a diagnosis for an event based on signs, symptoms, and/or other clinical information. It is important to distinguish that individual signs and symptoms of the event are not adverse events and should not be reported.

For each AE, the Investigator will evaluate the causality and severity, report the action taken and event outcome and disclose whether or not it caused the subject to discontinue trial participation.

The following severity scale will be used as a guideline to differentiate the severity of adverse events:

- Mild (Grade 1): Transient or mild discomfort; no limitation in activity; no medical intervention/therapy required
- **Moderate (Grade 2)**: Mild to moderate limitation in activity some assistance may be needed; no or minimal medical intervention/therapy required
- Severe (Grade 3): Marked limitation in activity, some assistance usually required; medical intervention/therapy required and often requiring hospitalization or prolongation of hospitalization
- Life-Threatening or Disabling (Grade 4): Extreme limitation in activity, significant assistance required; significant medical intervention/therapy required; hospitalization, prolongation of hospitalization, or hospice care
- Fatal (Grade 5)

An AE that is assessed as severe should not be confused with an SAE. Severity is a category utilized for rating the intensity of an event. An event is described as "serious" when it meets one of the pre-defined outcomes noted in Section 13.2.1.2. Both an AE and SAE can be assessed as severe. However, an AE of severe intensity may not meet SAE definition requirements.

#### 13.2.4. Reporting Adverse Events

All adverse events are collected from the time of signing informed consent for trial participation until completion of 6 months or early termination, whichever occurs first. All AEs occurring after the initiation of the IV catheter placement for the initial dose of CAP-1002 will be considered treatment emergent. Any ongoing adverse event that has not been resolved at the time of trial completion or early termination for a subject will be marked as ongoing on the adverse event case report form (CRF).

All AEs will be entered into the electronic data capture (EDC) system by trained site personnel at the investigative site.

Expected and unexpected SAEs must be reported to Capricor and entered into the EDC system within 24 hours of discovery of the event. For events that do not have complete information available at the time of initial report, the investigative site will submit all available information at the time of the submission. All SAE Report Forms must be signed by an Investigator and submitted with available source documentation. All source documentation must be de-identified prior to submission.

ALL SAES and subsequent follow-up information must be reported to Capricor, or designee, via email or fax as outlined in the Manual of Procedures and Safety Plan.

All SAEs must be reported to the respective IRB in accordance with the investigative site's policies. Copies of the submission will be collected by Capricor.

All SAEs will be reported to the DSMB at least semi-annually, or more frequently at the discretion of the Medical Monitor.

Capricor will promptly upon discovery, report serious and unexpected adverse events for which there is a reasonable possibility that the investigative therapy (i.e. administration product and/or investigative product) caused the events, to the Food and Drug Administration (FDA) in accordance with 21 CFR 312.32 regulations and ICG E2A guidelines.

For trials conducted under an investigational new drug (IND) application, FDA regulations require reporting of any suspected adverse reaction. A serious adverse reaction is defined as any adverse event for which there is a reasonable possibility that the drug/biologic caused the AE. For the purposes of IND safety reporting, "reasonable possibility" means there is evidence to suggest a causal relationship between the drug/biologic and the adverse event. Serious, unexpected suspected adverse reactions (SUSARs) are SAEs that are unexpected and are possibly or probably related to participation in the research. Expedited reporting is required for all SUSARs. Capricor will send an initial Expedited Safety Report (ESR) or MedWatch Form 3500A to the FDA within 5 business day of determination that the event qualifies for reporting.

#### 13.2.5. Pregnancy Reporting

Should a female be impregnated by a trial subject, investigative sites are required to notify Capricor within 24 hours of learning about the pregnancy. The investigative site will receive the Pregnancy Reporting Form to complete and submit to Capricor, or designee.

All pregnancies will be followed until the pregnancy outcome is known. In addition, pregnancies that are ongoing at the time of trial completion will be followed until the outcome is known. The investigative site is responsible for outcome reporting via the Pregnancy Reporting Form, including spontaneous or voluntary termination, details of birth, and the presence or absence of any birth defects, congenital abnormalities, or maternal and newborn complications.

The pregnancy is not an adverse event for the male subject unless there is a suspicion that the investigational product interfered with the effectiveness of a contraceptive medication.

#### 13.2.6. Adverse Event Follow-up

All AEs are followed by the investigative site until an outcome is known or the subject's participation in the trial concludes at either 6 months or early termination, whichever occurs first.

The investigative site is expected to review all ongoing AEs at each visit. AEs are followed until resolution or until no further changes in the event are expected (i.e., the point at which a subject experiencing an AE is treated successfully and stabilized even though he may continue to experience lingering sequelae that may never resolve), or it is agreed that further follow-up of the event is not warranted (e.g., non-serious, IP unrelated, ongoing at final visit). See Section 13.2.3 for reporting ongoing AEs at the end of trial participation.

For SAEs that were incomplete or ongoing at the time of initial submission, the investigative site is required to submit follow-up SAE Report Forms when event information is available to the research site personnel and/or an outcome is known.

# 14. STATISTICS

#### 14.1. General Considerations

- 1. Descriptive statistics will be used to summarize all subject baseline and outcome data collected during the trial. Continuous variables will be summarized using mean, standard deviations, medians, and ranges. Categorical variables will be summarized in frequency distributions or as rates.
- 2. Statistical analyses will be performed by validated software (e.g., SAS, IBM/SPSS, or Cytel Software).
- 3. There is no formal hypotheses or statistical tests associated with trial endpoints. Statistical tests will be performed, however, for informational value as part of summarizing trial results. Parametric and non-parametric tests will be used that are appropriate to the outcome measure being summarized. Reported p-values will be considered nominal and unadjusted for multiple testing, without conclusions regarding statistical significance levels.
- 4. Copies of databases used to prepare clinical report summaries will be archived to enable any statistical analyses performed to be replicated.
- 5. A full data listing will be prepared, including an electronic version in a standard computer-accessible format (e.g., SAS) at the completion of the study. Listings of data represented on the case report forms (eCRF) will be provided for all key baseline, demographic and outcome variables to facilitate further investigation of tabulated values and to allow for clinical review of safety variables.

# 14.2. Sample Size

Up to 10 subjects that were randomized to Usual Care Treatment Group and completed the 12month follow-up period for the HOPE-Duchenne trial will be enrolled in this trial.

# 14.3. Analysis Population

Intent-to-Treat (ITT) Population: All subjects who meet the enrollment criteria and are enrolled in the study. These subjects will also constitute the Safety population.

Per Protocol (PP) Population: All enrolled subjects who have no protocol deviations/violations that could significantly impact the completeness, accuracy and/or reliability of the trial data. The list of subjects in the per protocol population will be compiled prior to database lock.

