#### Analysis Populations

Intent-to-Treat (ITT) Population: All patients who meet the enrollment criteria and are enrolled in the trial. These patients will also constitute the Safety population.

Per Protocol (PP) Population: All enrolled subjects who have no protocol deviations/violations that could significantly impact completeness, accuracy, and/or reliability of the trial data. The list of subjects in the per protocol population will be compiled prior to database lock.

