# 7. INVESTIGATIONAL PLAN

## 7.1. Overall Trial Design

This Phase 2, multi-center, open label extension trial will provide CAP-1002 to subjects who were randomized to the Usual Care Treatment Group and completed 12 months of follow-up in the HOPE-Duchenne trial. The trial will assess the safety of CAP-1002, administered as two IV infusions, each separated by 3 months. All subjects will undergo targeted tests and procedures within 30 days prior to first infusion, unless otherwise stated, to confirm eligibility based on protocol inclusion and exclusion criteria.

Eligible subjects will undergo baseline safety and efficacy assessments (Table 3) prior to the first infusion of CAP-1002. Administration of CAP-1002 (Day 1) should occur within a maximum of 14 days following confirmation of eligibility; if a delay of more than 14 days between enrollment and CAP-1002 administration is unavoidable, a conversation between the Investigator and Medical Monitor should occur to determine the need for repeat assessments prior to infusion. For the purposes of this trial, enrollment is defined as the time consent is signed.

All intravenous infusions will be conducted in an outpatient setting at the investigative site on Day 1 and at Month 3. Subjects will be observed in the outpatient setting for at least two hours post infusion and then discharged the same day if medically cleared by the site Investigator.

A safety phone call will be performed 14 days ( $\pm 3$  days) after each CAP-1002 infusion, and if clinically indicated, an unscheduled in-person visit will be performed at the investigative site with targeted assessments based on presentation of signs and symptoms.

Blood samples will be collected at Week 4 and Month 4 ( $\pm$ 7 days, respectively) for DSA testing and safety laboratory assessments. Collection will occur either at the investigative site or remotely at a designated central laboratory patient service center.

Subsequent trial visits at the investigative site will occur at Months 3 and 6 ( $\pm$ 14 days, respectively). Subjects will complete safety and efficacy assessments at each of these visits and prior to CAP-1002 administration in the case of the Month 3 trial visit.

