## 8.3. Screen Failures

Any subject who provides written informed consent/assent and is ultimately not infused for whatever reason will be classified as a screen failure. All subjects, including screen failures, must be accounted for in the clinical database.

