# 14.5. Efficacy Analysis

Efficacy will be evaluated at the 3 and 6-month follow-up visit, with changes from baseline assessed for pre-specified exploratory endpoints. Analyses will be performed both in the ITT and PP populations.

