## 4.4 Analysis Populations

The following analysis populations will be defined.

- Intent-to-Treat (ITT) Population: The Intent-to-Treat (ITT) population will be defined as all subjects who meet the enrollment criteria and are enrolled in the study.
- Safety Population: The Safety population will be defined as all subjects who receive any amount of IP.
- Per Protocol (PP) Population: The PP population will include subjects who have no protocol deviations/violations that could significantly impact the completeness, accuracy and/or reliability of the trial data. The list of subjects in the per protocol population will be compiled prior to database lock.

A summary of the number and percentage of subjects in each analysis population will be provided. A listing of subject assignment into each analysis population will also be displayed.

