# 5 STUDY POPULATION PARAMETERS

The study population parameters to be listed and summarized are described below. The ITT population will be used for the listings and summaries. Some of the summaries may also be done for other analysis populations defined in Section 4.4.

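### The protocol and the SAP define the Safety population differently, and if an ineligible subject is infused, no planned efficacy set is guaranteed to include everyone treated

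*Protocol*

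**What the plan says.** **Safety set.** Protocol 14.3 defines ITT as "All subjects who meet the enrollment criteria and are enrolled in the study" and adds "These subjects will also constitute the Safety population". The synopsis repeats the rule: "These patients will also constitute the Safety population". SAP 4.4 keeps the same ITT definition but separates the Safety set: "The Safety population will be defined as all subjects who receive any amount of IP". SAP 7 runs the safety listings and summaries, including the primary safety endpoint table, on that set. The SAP does not flag the difference from the protocol.

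**Enrollment and screen failure.** Protocol 7.1 states: "For the purposes of this trial, enrollment is defined as the time consent is signed"; SAP 3 repeats it. Under protocol 8.3, anyone who consents and "is ultimately not infused for whatever reason will be classified as a screen failure".

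**Efficacy sets.** Protocol 14.5: "Analyses will be performed both in the ITT and PP populations". SAP 6 says the same, and SAP 6.1 to 6.4 name no other set. PP is restricted by the absence of important deviations, with no infusion condition.

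**Other SAP rules that bear on this.**
- SAP 5, which covers the exposure summary in 5.12: "The ITT population will be used for the listings and summaries". Its next sentence permits some summaries in other sets.
- SAP 4.1 limits the presented treatment group to recipients of CAP-1002.
- SAP 4.2 anchors baseline to the first administration of product.
- SAP 5.14 tabulates, for ITT, reasons for not receiving product.

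**The concern.** Two approved documents give different denominators for the primary safety endpoints, and nothing says which prevails. The protocol's set can be wrong in both directions. It can count a subject with no exposure, whom the same protocol calls a screen failure, and it can omit a subject who was exposed. In an uncontrolled trial of up to 10 subjects, whose safety result is a list of incidences, one subject decides whether an event appears in the numerator.

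The SAP repairs the Safety set but leaves efficacy unchanged. Both efficacy sets carry a restriction other than treatment: ITT requires eligibility, and PP requires the absence of important deviations. A subject infused despite failing a criterion is outside the first and may be outside the second. The SAP lists inclusion/exclusion among its possible deviation categories (5.3), so the case is at least contemplated. By default the same subject is also missing from the exposure summary in SAP 5.12.

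**Working it through.** The plan gives no derivation for its sample size of up to 10, so there is no figure to reproduce. The check compares the set definitions and then illustrates them with assumed counts.

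**Membership as written**

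| Subject | ITT (both documents) | Safety, protocol | Safety, SAP |
|---|---|---|---|
| Eligible, consented, infused | in | in | in |
| Eligible, consented, never infused | in | in | out |
| Infused, did not meet criteria | out | out | in |
| Ineligible, never infused | out | out | out |

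The two Safety sets disagree in the second and third rows.

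**Assumed counts.** Take 10 consented subjects (the planned maximum is from protocol 7.3). Let u be the number eligible but never infused, and v the number infused without meeting the criteria. Everyone else is eligible and infused.

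- SAP Safety set (all treated) = 10 − u
- ITT = protocol Safety set = 10 − v
- Treated subjects inside ITT = 10 − u − v
- Share of treated subjects inside ITT = (10 − u − v)/(10 − u)

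| u | v | SAP Safety | Protocol Safety = ITT | Treated in ITT | Share |
|---|---|---|---|---|---|
| 0 | 0 | 10 | 10 | 10 | 100% |
| 1 | 0 | 9 | 10 | 9 | 100% |
| 2 | 0 | 8 | 10 | 8 | 100% |
| 0 | 1 | 10 | 9 | 9 | 90% |
| 1 | 1 | 9 | 9 | 8 | 8/9 = 88.9% |
| 2 | 2 | 8 | 8 | 6 | 6/8 = 75% |

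Equal totals do not mean equal sets. At u = 1, v = 1 both Safety sets have 9 members, but not the same 9.

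**Effect on an incidence** (exact Clopper-Pearson 95% intervals)

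- u = 2, v = 0, one event in an eligible infused subject. Protocol: 1/10 = 10.0% (0.3% to 44.5%). SAP: 1/8 = 12.5% (0.3% to 52.7%).
- u = 0, v = 1, the one event in the ineligible infused subject. Protocol: 0/9, with upper limit 1 − 0.025^(1/9) = 33.6%. SAP: 1/10 = 10.0% (0.3% to 44.5%).

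In the first case the denominator moves by two. In the second, an observed event drops out of the summary.

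**Effect on mean changes.** A never-infused subject has no baseline under SAP 4.2 and so no change from baseline. Within ITT, u therefore alters counts but not mean changes. Only v alters the efficacy means, by removing treated subjects.

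**The case against.** The strongest reply is that the tables will be built from the SAP. Its safety outputs use the any-amount-of-IP set, and SAP 4.1 presents only recipients of CAP-1002. If the SAP is followed, safety incidence is neither diluted nor missing an exposed subject. This stands: a reader might infer that the reported safety rates will be wrong, and the documents do not support that. The fault is in the protocol text and in the unflagged disagreement.

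Second, a reader might infer that no efficacy set ever covers everyone treated. That is too strong. If no ineligible subject is infused, ITT contains all treated subjects. PP could keep an infused ineligible subject if the deviation is judged unimportant, although PP may drop others. The gap is conditional.

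Third, a reader might infer a deliberate route for removing treated subjects from ITT after their results are seen. No passage says this. Eligibility is assessed at screening and Day 1 and confirmed before infusion, so meeting the criteria can be read as status at that time. Protocol 17.5 has the Medical Monitor and the biostatistician review whether data affected by deviations can be included, but it does not say that ITT membership is reopened. What stands is an ambiguity: only the PP list has a stated deadline, before database lock.

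Fourth, listings cover all subjects (SAP 4), so an omitted subject's data would still be visible. The donor-specific antibody section (SAP 5.8) specifies listings, so it needs no change. Efficacy is exploratory and descriptive, with no formal hypotheses. These points limit the consequence, but they do not reconcile the two Safety definitions or restore an infused ineligible subject to the efficacy summaries.

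**Conclusion.** The point holds in a limited form. The protocol (14.3 and synopsis) and SAP 4.4 contradict each other on the set that carries the primary safety endpoints, and the protocol's version can both include unexposed subjects and omit exposed ones. The SAP's version does neither. For efficacy, the shared ITT wording leaves no set guaranteed to contain all treated subjects once an ineligible subject has been infused. Never-infused subjects affect counts only.

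The size depends on events that may not occur. With u = v = 0, ITT and both Safety sets are identical. With one infused ineligible subject out of 10, ITT covers 90% of those treated, and an event in that subject reads 0/9 under the protocol and 1/10 under the SAP. These counts are assumptions for illustration; the documents give no expected number of either kind of subject. The change should be made because it is a plain inconsistency with a simple remedy. Nothing here shows that the safety results will be misreported.

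**What to change.** 1. **Protocol 14.3 and synopsis:** replace the Safety definition with the SAP's, all subjects who receive any amount of IP. Treatment emergence starts at catheter placement for the first dose (protocol 13.2.4, SAP 7.1), so a subject could have a treatment-emergent event and then receive no product. List any such event separately.
2. **Protocol 14.3 and 14.5, SAP 4.4 and 6:** make the main efficacy set the same treated set, regardless of eligibility deviations, in place of the present ITT wording. Using one rule for safety and efficacy avoids a second mismatch. Keep PP as the restricted set.
3. **SAP 5.12:** base the exposure summary on the Safety population. SAP 5.8 needs no change.
4. **Protocol 7.1 and 8.3, SAP 3 and 4.1:** reconcile enrollment at consent with the rule that any consented, never-infused subject is a screen failure, and with the restriction of the presented group to recipients. State where an eligible, never-infused subject is counted in disposition.

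The cost is wording in the two documents. No additional data, visits or subjects are needed.

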# 14.4. Safety Analysis

#### 14.4.1. Safety Endpoints

All primary safety endpoints and other observed adverse events will be documented and reported. Adverse events will be summarized by the incidence of events by type and by the percentages (rates) of subjects with those events. Primary safety endpoints that are adjudicated by the Clinical Events Committee (CEC) will be further described by the relatedness to the study treatment and severity level.

#### 14.4.2. Medications

A listing of prescription and over the counter medications used by individual trial subject will be prepared, including information on generic name. dosage, frequency of administration, reason for use, observed side effects, and any related adverse events. Study level summaries by type of medication may also be prepared.

#### 14.4.3. Clinical Laboratory Evaluations

All laboratory evaluations will be documented. A listing of results by subject will be prepared, with any abnormalities noted at baseline or during the follow-up period.

#### 14.4.4. Donor-Specific Antibodies

Donor-specific antibodies (DSA) will be assessed as screening and periodically during the follow-up period or upon clinical suspicion of an immune sensitization response, and will be summarized by the specific CDC donors contributing to the CAP-1002 doses used by individual subjects.

#### 14.4.5. Physical Examination

Medical status and baseline physical exam results, including vital signs, 12-lead ECG, and weight, will be summarized using descriptive statistics and any observed abnormalities. Any changes over the follow-up period will be documented and reported.

# 14.5. Efficacy Analysis

Efficacy will be evaluated at the 3 and 6-month follow-up visit, with changes from baseline assessed for pre-specified exploratory endpoints. Analyses will be performed both in the ITT and PP populations.

# 14.5.1. Exploratory Efficacy Endpoints

Descriptive statistics will be used to summarize changes from baseline in the PUL 1.2 scores (including the mid-level dimension, combined mid and distal-level dimensions, and high-level dimension), in left ventricular structure and function parameters (including ejection fraction, wall thickness, end-diastolic and end-systolic volumes, stroke volume, and circumferential strain, in pulmonary function (including SVC, FEV1, FVC, MIP, MEP, PCF, and IFR) and in 6-minute walk test distance for ambulatory subjects.

